#### **5.4.2 *Masking Procedures***

In this RCT, it is not feasible to blind patients, surgeons, or dental assistants to treatment after the intervention assignments have occurred, so they will not be blinded. It is, however, feasible to mask the sequence of treatment assignments until the moment each assignment is made, and this will be done, as described in Section 5.4.1, above.

The DCC will also be un-blinded to treatment arm assignment. However, study staff and investigators will not have access to any interim outcome data. Unmasking procedures during the surgery will not be necessary as the patient, surgeon, and dental assistants will be un-blinded to the treatment group for each patient. The patient's record in the OMS office will include documentation of study participation and their group assignment (i.e., UC versus EC).

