Patient-reported data will be collected via tablets, smart-phones, or computers at baseline during in-office visit(s) with the surgeons. To assist with in-office data collection, participating OMS will be offered tablets. OMS, dental assistants, and patients will provide baseline and follow-up data directly into the electronic data capture (EDC) system that is maintained by the HealthPartners Data Coordinating Center (DCC); data can be entered via tablets, smart-phones, or computers. After baseline, patient-reported data will be ascertained independent of office visits, and all follow-up patient, OMS and dental assistant data collection will be managed by HP DCC. Follow-up contacts to non-responders will also be managed by the DCC.

- **Overview of Study Schedule**

- The electronic data system used to collect patient and OMS/dental assistant data will be assessed for acceptability and compatibility prior to administration of any questionnaires.
- OMS and their office staff will receive study training from the Study Coordinator (SC), after which the OMS is authorized to begin enrolling study patients.
- An in-office patient log will be kept regarding the reason patients were excluded or declined to participate.
- Once the patient is screened using the *Screening Questionnaire* that comprises the inclusion and exclusion criteria, patients who are eligible will be invited to participate in the study. Potential patients who are interested in study participation will undergo consent procedures.
- Patients will complete these baseline forms and questionnaire before surgery: *Patient Contact and Patient Demographics information*, and *Patient Baseline Questionnaire*.
- Randomization procedures will occur, and patients will receive their randomized assignment.
- The OMS will complete the *Doctor Surgery Questionnaire* after completing the 3rd molar extractions.
- At 1, 3, and 6 months post-baseline, patients will complete follow-up assessments via an online questionnaire. Non-responders will be followed up with email, telephone, and/or texting. All patients will be followed up regardless of whether they report TMD pain at any follow-up.

- Midway through and at the end of the enrollment phase of the study, the OMS and dental assistants will complete a questionnaire regarding their experience with the use of the device.

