### **First Month Follow-up of Study Patients by study staff**

Patients will receive emails with active links to the online web-based *Patient One-month Follow-up Questionnaire* for electronic completion. The DCC will attempt email, telephone and/or text contact for non-responders to remind them to complete the questionnaires online or over the telephone. Completion of questions over the telephone is an option for those patients who do not complete the form by close of data collection window.

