### **5.3 Strategies for Recruitment and Retention**

All patients presenting to participating surgeons' practices will be considered for eligibility. For patients without TMD pain in the last 3 months, the surgeons or their office staff will discuss the study and review eligibility criteria with the patient. Patients who meet eligibility criteria and consent to participate in the study will complete their baseline data collection forms, undergo randomization procedures, and then have their 3rd molars surgically removed.

Patients will be told that their treatment will not be affected by participation in the study except that they will be randomized to UC or EC.

Patient retention is important to this study, and follow-up data will be collected independently of in-office visits. Study patients will be asked to complete follow-up assessments online at 1-, 3-, and 6- months after the baseline visit. Patients will be paid \$125 total for completed questionnaires; \$25 at baseline, \$25 at 1-month follow-up, \$25 at 3-month follow-up and \$50 at the 6-month follow-up.

Study patients will be contacted by email prior to each data collection time point at 1-, 3-, and 6-months post-surgery. The initial email contact for each survey period will contain the request to complete the questionnaire and an active link to the online web-based questionnaire. Email, telephone and/or text follow-up attempts will be implemented for non-responders. The HealthPartners DCC will email, call and/or text patients who do not complete the follow-up questionnaires by the close of the target data collection window to encourage them to complete surveys. When contacted, patients will be given the option to complete the questionnaire by telephone with the DCC.

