#### **5.4.1 Randomization Procedures**

The OMS or dental assistant will provide a participant with the randomization assignment after the participant's eligibility is confirmed and his/her consent is obtained. The random assignment will be obtained from the study tablet used by the OMS or dental assistant. The study tablet, which will be programmed by the HP DCC, will (among other things) use randomized treatment assignments from a stratum-specific

(i.e., surgeon-specific) sequence of randomized assignments created as described in the following paragraph. Each surgeon-specific randomization sequence will be loaded into the tablet by the programmer at the HP DCC in such a way that it will be impossible for clinical study personnel, in particular for the OMS or dental assistant to access this sequence or to infer any treatment assignment in the sequence until the moment that assignment is given to a particular participant.

For each stratum (i.e., surgeon), the randomization sequence will be created by the project statistician using custom-written code in the R system (R Foundation for Statistical Computing, Vienna, Austria, <https://www.R-project.org/>), as follows: The sequence will use randomized permuted blocks of size 2 and 4, in each of which the two treatments are present equally often. The R code will first generate a random sequence of block lengths, so that study personnel will never be able to tell which block they are in, and then in each block, the treatment assignments will be randomly permuted, so that each sequence of possible treatments within a block is equally probable.

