#### OMS – Baseline:

- The OMS will complete the *Doctor Surgery Questionnaire* for each of the consented patients in both the EC and UC groups after the surgery is completed. The target is to have the OMS complete the questionnaire on the day of the surgery. This questionnaire assesses: 1) TMD pain present in the last 3 months, 2) any TMJ noise present, 3) information on surgical procedures (e.g., teeth extracted, eruption status, presence of pericoronitis or

infection, reason for extraction, procedure employed for removal, estimate of time to extract the tooth and sequence of extractions). In addition, if the device was used, OMS will record whether the use of the device was discontinued during the surgery.

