## **16 DATA HANDLING AND RECORD KEEPING**

The study team is responsible for ensuring the accuracy, completeness, legibility, and timeliness of the data reported. All source documents should be completed in a manner to ensure accurate interpretation of data. The investigators will maintain adequate case histories of study subjects, including accurate case report forms (CRFs) and source documentation.

Only study personnel (i.e., PI, Co-Investigator's, study statistician, study coordinator, and DCC personnel) will have access to the study data elements in the study database as described in Section 16.3 Types of Data. All study personnel will have completed the human subjects' protection training elements as required by their IRB.

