### **16.2 Data Capture Methods**

This study will utilize a centralized electronic data capture (EDC) system, developed and maintained by the DCC, for practitioners and patients to enter data onto web-based CRFs. The EDC system employs on-screen data validation utilizing univariate and multivariate alerts, as needed, including valid-value, valid-range, and missing-value alerts. These validations will prevent users from continuing with study data collection if invalid or missing data entries are provided.

The EDC system provides comprehensive and extensible support for both Authentication and Authorization through role-based access control. Access to the EDC system will be available to specific study team members, site study staff and DCC study staff. Staff eligible to access the web application will be assigned an application-specific

user account and will create a unique password to access the application. All access to the systems is based on authorization by the PI and/or the DCC manager or their delegates. Access to sections within the EDC application will be role-based, thereby limiting the user's access only to pertinent information for their role with patients at their assigned study site.

Practitioner- and patient-entered information on CRFs through the application is transmitted to and stored in the EDC system essentially in real time. While practitioners can access the web application, and practitioners and patients can access web-based CRFs, only key study and DCC staff will have direct access to core EDC system and its data. Therefore, each user of the EDC system is permitted access to only the minimum necessary data required to fulfill their role in the study.

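### Section 5.4.2 un-blinds the DCC without excepting any role, yet the DCC may take the self-report outcome questionnaire by telephone; the protocol should state that callers are masked and record the mode of completion.

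*Combined protocol and SAP*

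**What the plan says.** On masking, Section 5.4.2 explains that patients, surgeons and dental assistants cannot feasibly be blinded. It then adds, with no reason and no exception: "The DCC will also be un-blinded to treatment arm assignment". The limit that follows concerns access to interim outcome data. It does not concern who knows the arm.

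On follow-up, Section 4 (Data Collection) says that "all follow-up patient, OMS and dental assistant data collection will be managed by HP DCC". Online completion is the default. For non-responders, Section 5.3 has the DCC email, call or text, and "patients will be given the option to complete the questionnaire by telephone with the DCC". Section 4 gives the same fallback at month 1 ("Completion of questions over the telephone is an option for those patients who do not complete the form") and repeats the procedure at months 3 and 6.

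On outcomes, Section 3.2.1 defines the primary outcome by self-report in these questionnaires: endorsing one or both of two pain items. The between-arm secondary outcomes in Section 3.2.2 (items 1 to 3) come from the same questionnaires.

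On access, Section 16.2 says "each user of the EDC system is permitted access to only the minimum necessary data required to fulfill their role in the study", and Section 15.5 says much the same. Section 16 limits database access to listed study roles; the list ends "DCC personnel) will have access to the study data elements in the study database as described in Section 16.3 Types of Data". Section 16.3 includes the Doctor Surgery Questionnaire, in which, according to Section 8.1, "if the device was used, OMS will record whether the use of the device was discontinued during the surgery".

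**The concern.** In an open-label trial with self-reported outcomes, patients' knowledge of their arm cannot be removed. The protocol discloses this, and it is not the issue here. An interviewer's knowledge of the arm is a separate matter. A caller can influence a yes/no pain item through phrasing, probing, or the coding of a hesitant answer. If that influence differs by arm, it enters the treatment comparison directly.

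Section 5.4.2 itself masks what can feasibly be masked, namely the allocation sequence. Caller masking also looks feasible with the access controls already described, but the protocol does not state it. Taken literally, Section 5.4.2 lets the person recording the primary outcome know the arm.

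**Working it through.** **Step 1: the passages side by side.**

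| Question | Where | Answer |
|---|---|---|
| Is the DCC masked? | 5.4.2 | No; no role excepted |
| Who manages follow-up collection? | 4 | The DCC |
| Can the DCC take answers by telephone? | 5.3; 4 | Yes, from non-responders, at months 1, 3 and 6 |
| Do those answers form the primary outcome? | 3.2.1, 12.4 | Yes |
| Are callers said to be masked? | 5.4.2, 15.5, 16, 16.2 | Not stated; the access text mentions neither arm nor callers |
| Does any DCC role need the arm? | 5.4.1 | Yes: "Each surgeon-specific randomization sequence will be loaded into the tablet by the programmer at the HP DCC" |

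**Step 2: reproduce the plan's design figure.** Inputs from Section 12.2: incidence 14%, relative risk 2.0 (so 28% versus 14%), two-sided 0.05, 80% power. The mean rate is 0.21.

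n = [1.96√(2×0.21×0.79) + 0.8416√(0.14×0.86 + 0.28×0.72)]² / 0.14² = (1.1290 + 0.4776)² / 0.0196 = 131.7, so 132 per arm. Power at 132 is 80.1%, and 264/0.90 = 293.3, so 294. All match the plan.

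**Step 3: illustrate the possible size.** The documents give neither the telephone share f nor the difference d between arms that callers might cause among telephone answers. Assumed here: f = 10%, 20%, 30%; d = 5 or 10 points. The net shift is s = f × d, from 0.10 × 5 = 0.5 points to 0.30 × 10 = 3 points.

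For a two-proportion z-test with 132 per arm, let Δ be the difference between the recorded rates p₁ and p₂, and p̄ their mean:

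- SE₀ = √(2p̄(1−p̄)/132)
- SE₁ = √((p₁(1−p₁) + p₂(1−p₂))/132)
- rejection probability = Φ((Δ − 1.96 SE₀)/SE₁) + Φ((−Δ − 1.96 SE₀)/SE₁)

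The null columns put the usual care arm at the base rate and the device arm s lower. The power columns compare 28% with 14% + s (shift against the device) or 14% − s (shift in its favor).

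Worked cases at s = 3 points:

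- Null at 28% (28% versus 25%): SE₀ = 0.05432, SE₁ = 0.05429; Φ(−1.41) + Φ(−2.51) = 0.0795 + 0.0060 = 0.0855.
- Null at 14% (14% versus 11%): SE₀ = 0.04071, SE₁ = 0.04067; 0.1104 + 0.0035 = 0.1139.
- Power, shift against the device (28% versus 17%): (0.11 − 1.96×0.05140)/0.05095 = 0.18, giving 57.2%.
- Power, shift in its favor (28% versus 11%): (0.17 − 1.96×0.04877)/0.04763 = 1.56, giving 94.1%.

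| f, d (points) | s (points) | False positive, 28% rate | False positive, 14% rate | Power, against device | Power, favoring device |
|---|---|---|---|---|---|
| none | 0 | 5.0% | 5.0% | 80.1% | 80.1% |
| 10%, 5 | 0.5 | 5.1% | 5.2% | 76.8% | 83.2% |
| 10%, 10 or 20%, 5 | 1.0 | 5.4% | 5.6% | 73.2% | 85.9% |
| 30%, 5 | 1.5 | 5.9% | 6.5% | 69.4% | 88.4% |
| 20%, 10 | 2.0 | 6.5% | 7.7% | 65.5% | 90.6% |
| 30%, 10 | 3.0 | 8.5% | 11.4% | 57.2% | 94.1% |

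The gain in the last column is nominal: it comes from biased recording. If the null shift runs the other way (device arm higher), the top values are slightly smaller, 8.3% at the 28% rate. The planned GEE over three visits (Section 12.4) would give somewhat different figures.

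**The case against.** The strongest reply is that Section 5.4.2 openly discloses who is un-blinded, that some DCC work needs the arm, and that minimum-necessary access would already keep the arm from a caller, who does not need it to read out a pain questionnaire. The operating detail may also sit in the Manual of Procedures or the Data Management Plan, which are not available here. Much of this stands. It makes caller masking plausible, but it does not state it. General access wording that never mentions the arm does not clearly override a specific sentence that un-blinds the DCC. The Supplemental Materials page also says that the Data Management Plan is outside the protocol and can change without an amendment.

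A second reply is that patients know their arm anyway, so masking callers gains little. That limits the benefit: patient reporting bias remains, and a patient may reveal the arm during the call. Interviewer influence is still a separate source that can be reduced.

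A third reply is that the telephone share and the caller effect are invented. They are assumptions, and at 10% telephone use the false-positive rate barely moves.

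A reader might infer that Section 16 positively gives callers the arm, because it names DCC personnel and the Doctor Surgery Questionnaire can reveal device use. The documents do not support that. The sentence restricts access to listed study roles and, read with Sections 15.5 and 16.2, leaves the question open. A reader might also infer that no check is possible because every between-arm efficacy outcome is self-report. That goes too far: online answers involve no interviewer, so comparing the arms among online completions is a partial check, though open to selection.

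**Conclusion.** The point holds as a gap that should be closed. The protocol un-blinds the DCC without exception, lets the DCC take the primary-outcome questionnaire by telephone, and does not say that callers are masked. This permits a partly avoidable interviewer bias.

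Its size is unknown. Under the assumed shares and differences, the false-positive rate runs from about 5.1% to 8.5% at a 28% rate and from 5.2% to 11.4% at a 14% rate. Nominal power runs from about 57% to 94% around the planned 80%. These figures are not bounds, and the effect is small unless telephone completion is common.

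The documents do not show that callers will in fact know the arm, and they do not indicate which arm any shift would favor. A conclusion that the result will be biased toward the device is therefore not supported.

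**What to change.** 1. In Section 5.4.2, replace the blanket sentence. Limit un-blinding to the DCC roles that need the arm, for example the programmer who loads the sequence (Section 5.4.1). State that DCC staff who contact patients or take questionnaires by telephone are masked to arm.
2. State that this is done through the role-based access in Section 16.2, and that it hides from those staff both the assignment and the device-use item of the Doctor Surgery Questionnaire. Align the DCC access sentence in Section 16. If the Manual of Procedures or Data Management Plan already provides this, say so in Section 5.4.2.
3. Record for each questionnaire whether it was completed online or by telephone. Add to Section 12.4 a sensitivity comparison of the arms among online completions, noting that this subset is selected after randomization.

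The cost is a few sentences, one access setting and one data field. Masking will be imperfect because patients may disclose their arm, and the DCC must keep caller roles separate from roles that need the arm.

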### **5.5 *Subject Withdrawal***

#### **5.5.1 *Reasons for Withdrawal***

Patients may withdraw voluntarily from participation in the study at any time upon request, including at baseline and at any follow-up time points.

An investigator may terminate a study patient's participation in the study if:

- Any clinical adverse event (AE) or other medical condition or situation occurs such that continued participation in the study would not be in the best interest of the patient. All patients who provide consent and are randomized to one of the treatment arms will remain in the study even if they are not able to follow through with their group assignment through the completion of the surgical procedure. This includes an event that occurs during the surgical removal of their 3rd molars that precludes completion of the surgical procedure at that time. Only patients who no longer consent to provide data will be withdrawn.
- The patient meets an exclusion criterion (either newly developed or not previously recognized) that precludes further study participation.
- If an enrolled patient declines to provide any of the essential baseline data on the Patient Contact Form, the Patient Demographics Form, and/or the Baseline Patient Questionnaire, this decision will be considered a voluntary withdrawal from the study by the patient and the PI will withdraw the patient from the study.

#### **5.5.2 *Handling of Subject Withdrawals or Subject Discontinuation of Study Intervention***

All patients who provide consent and are randomized to one of the treatment arms will continue to provide data unless and until they explicitly withdraw their consent for further data collection. Only participants who no longer consent to provide data will be excluded from further data collection, and data collected during the duration of their participation will be included.

For patients who cease to receive their assigned treatment or who withdraw from study participation, the date and reason for this change in status will be recorded. Patients who have withdrawn consent for study participation may continue to receive usual care as patients of the participating OMS.

OMS will not replace patients who have withdrawn from the study; the study's sample size was chosen to account for 10% of patients not providing follow-up data.

If any OMS or DA withdraws from study participation, he/she will be replaced, and the replacement(s) will be trained on study procedures prior to participating in the trial.

#### **5.6 Premature Termination or Suspension of Study**

This study may be suspended or prematurely terminated if there is sufficient reasonable cause. Written notification, documenting the reason for study suspension or

termination, will be provided by the suspending or terminating party to the investigator, funding agency and regulatory authorities. If the study is prematurely terminated or suspended, the principal investigator will promptly inform the IRB and will provide the reason(s) for the termination or suspension.

Circumstances that may warrant termination include, but are not limited to:

- Determination of unexpected, significant, or unacceptable risk to patients.
- Insufficient adherence to protocol requirements.
- Data that are not sufficiently complete and/or evaluable.
- Determination of futility.

## 6 STUDY INTERVENTION

[figure not shown]
### 6.1 Study Product Description

#### ***Description of the Restful Jaw Device (RJ2)***

The RJ2 device is used to support the jaw during dental procedures including surgical removal of 3rd molars (wisdom teeth) with moderate/deep sedation or general anesthesia. The device is designed to counter the downward forces placed on the mandible by clinicians during dental procedures and prevent jaw hyperextension (opening too wide) while providing a secure, stable jaw position.

Figure 1 shows a side view of the device mounted to the head rest post with the jaw brace (#5) under the patient's jaw

**Figure 1.** Side view of device mounted to the chair head rest

[figure not shown]

The device is designed to replicate the dental assistant's shoulders, arms, wrists and hands. The device has 5 components (see Figure 1): the first component is the *mounting assembly* that attaches the device to the dental head rest post (Figure 1. #1). The second component is the *split sphere assembly* which replicates the movements of the dental assistant's shoulder (Figure 1. #2). The third component is the “*arm*” of the device, replicating the dental assistant's arms, which can be rotated and moved in and out of the split ball assembly (Figure 1. #3). The fourth component is the *ball joint assembly* which replicates movements in the dental assistant's wrist (Figure 1. #4). The fifth component is the *padded jaw brace assembly* that replicates the dental

assistant's hands (Figure 1. #5). Please refer below to the “*Instructions for Use*” for more details regarding the device.

This device requires pressurized air to operate. Air hoses are provided with the device to connect it to the air supply in the surgical suite. If there is no air supply available, then a free-standing air compressor or pressurized tank is used. The control box that sits on the floor is where the air into and out of the device is controlled. The air hoses from the air compressor or tank connect to the “input” port on the control box. The 4 “output” ports on the control box connect, via hoses, to the shoulder and end of each arm (Figure 2, purple circles).

**Figure 2.** Device Air Valves

A foot switch is used to activate the device (pressurize the system) and to deactivate the device (remove pressure from the system). The foot switch is attached via tubing to the control box port. A pressure gauge is present on the control box to verify the pressure in the system. An emergency stop (e-stop) button is also present on the control box in the event of an emergency to evacuate all air from the system.

